MNAR	Missing Not at Random
N	Number (typically refers to subjects)
NIH	National Institutes of Health
OCO	Ordinal Clinical Outcome
OCOs	Ordinal Clinical Outcomes
PCT	Procalcitonin
PI	Principal Investigator
PT	Preferred Term
RADAR	Response Adjusted for Days of Antibiotic Risk
SAE	Serious Adverse Event
SAP	Statistical Analysis Plan
SD	Standard Deviation
SDCC	Statistical and Data Coordinating Center
SMC	Safety Monitoring Committee
SOC	System Organ Class
SOP	Standard Operating Procedures
U	Units
UADE	Unanticipated Adverse Device Effect
WBC	White Blood Cell
WHO	World Health Organization

1. PREFACE

The Statistical Analysis Plan (SAP) for “Targeted Reduction of Antibiotics Using Procalcitonin in a Multi-center, Randomized, Double-Blinded, Placebo-Controlled Non-Inferiority Study of Azithromycin Treatment in Outpatient Adults with Suspect Lower Respiratory Tract Infection (LRTI) and a Procalcitonin (PCT) Level of ≤ 0.25 ng/mL (TRAP-LRTI)” (DMID Protocol 15-0020) describes and expands upon the statistical information presented in the protocol.

This document describes all planned analyses and provides reasons and justifications for these analyses. It also includes sample tables, listings, and figures planned for the final analyses. Regarding the final analyses and Clinical Study Report (CSR), this SAP follows the International Council on Harmonisation of Technical Requirements for Registration of Pharmaceuticals for Human Use (ICH) Guidelines, as indicated in Topic E3 (Structure and Content of Clinical Study Reports), and more generally is consistent with Topic E8 (General Considerations for Clinical Trials) and Topic E9 (Statistical Principles for Clinical Trials). The structure and content of the SAP provides sufficient detail to meet the requirements identified by the Food and Drug Administration (FDA) and ICH, while all work planned and reported for this SAP will follow internationally accepted guidelines published by the American Statistical Association and the Royal Statistical Society for statistical practice.

This document contains: (1) a review of the study design, (2) general statistical considerations, (3) comprehensive statistical analysis methods for efficacy and safety outcomes, and (4) a list of proposed tables and figures. Within the table, figure, and listing mock-ups (Appendices 1, 2, and 3), references to CSR sections are included. Any deviation from this SAP will be described and justified in the CSR, as appropriate. The reader of this SAP is encouraged to also review the study protocol for details on conduct of the study and the operational aspects of clinical assessments.

2. INTRODUCTION

This is a randomized, double-blinded, placebo-controlled, non-inferiority multicenter clinical trial of azithromycin vs. placebo in adults presenting as outpatients with suspect LRTI and a PCT level of ≤ 0.25 ng/mL, as a strategy for reducing antibiotic prescriptions. The study is designed and powered for the primary analysis of a comparison of the efficacy of azithromycin versus placebo on Day 5 (i.e., after 4 days of treatment) in subjects with suspect LRTI and PCT levels of ≤ 0.25 ng/mL at enrollment using a non-inferiority approach. Subjects with a PCT value ≤ 0.25 ng/mL are randomized 1:1 to either enter a 5 day course of oral azithromycin or matching placebo. Randomization is stratified by clinical site. Subjects with a PCT > 0.25 ng/mL remained enrolled for chart review but were not to be randomized to receive study drug.

The study follows a variety of clinical improvement criteria for the primary endpoint as described in Section 3.3.

2.1. Purpose of the Analyses

Analysis of clinical improvement will be used to assess the efficacy of Azithromycin versus placebo. Non-inferiority of placebo versus azithromycin on Day 5 will be the primary analysis. The secondary outcome measures include Clinical Improvement on Days 11 and 28, and Response Adjusted for Days of Antibiotic Risk (RADAR) analysis. All components of clinical improvement and Desirability Of Outcome Ranking (DOOR) will also be analyzed individually.

3. STUDY OBJECTIVES AND ENDPOINTS

3.1. Study Objectives

3.1.1. Primary:

1. To compare the efficacy of azithromycin versus placebo on Day 5 (i.e., after 4 days of treatment) in subjects with suspect LRTI and PCT levels of ≤ 0.25 ng/mL at enrollment using a non-inferiority approach.

3.1.2. Secondary:

1. To compare groups receiving azithromycin versus placebo with regard to all antibiotic use by Days 11 and 28.
2. To compare groups receiving azithromycin versus placebo with regard to return visits to a physician's office or urgent care by Days 11 and 28.
3. To compare groups receiving azithromycin versus placebo with regard to emergency department visits by Days 11 and 28.
4. To compare groups receiving azithromycin versus placebo with regard to hospitalization by Days 11 and 28 if not hospitalized at the enrollment and randomization visit.
5. To compare groups receiving azithromycin versus placebo with regard to improvement in presenting symptoms by Days 11 and 28.
6. To compare the efficacy of azithromycin versus placebo on Day 11 in subjects with suspect LRTI and PCT levels of ≤ 0.25 ng/mL at enrollment using a non-inferiority approach.
7. To compare the efficacy of azithromycin versus placebo on Day 28 in subjects with suspect LRTI and PCT levels of ≤ 0.25 ng/mL at enrollment using a non-inferiority approach.
8. To compare the efficacy of azithromycin versus placebo in subjects with suspected LRTI and PCT levels of ≤ 0.25 ng/mL at Day 5 using a superiority approach, employing the RADAR methodology.
9. To compare groups receiving azithromycin versus placebo in regard to solicited events by Day 5.
10. To compare groups receiving azithromycin versus placebo in regard to hospitalization or visits to an Emergency Department (ED), outpatient clinic, or urgent care center for worsening or persistent LRTI after randomization by Day 5.
11. To compare groups receiving azithromycin versus placebo in regard to improvement in vital sign abnormalities or symptoms present at enrollment, on Day 5.
12. To compare groups receiving azithromycin versus placebo in regard to new vital sign abnormalities or symptoms on Day 5, or deterioration in symptoms relative to the enrollment visit on Day 5.

3.1.3. Exploratory:

1. To compare PCT levels at Day 1 and Day 5 among treatment failures in the placebo and azithromycin groups.
2. To compare the efficacy of azithromycin versus placebo in subjects with suspected LRTI and PCT levels of ≤ 0.25 ng/mL at Day 11 using a superiority approach, employing the RADAR methodology.

3. To compare groups receiving azithromycin versus placebo in regard to solicited events by Day 11.
4. To compare groups receiving azithromycin versus placebo in regard to hospitalization or visits to an ED, outpatient clinic, or urgent care center for worsening or persistent LRTI after randomization by Day 11.
5. To compare groups receiving azithromycin versus placebo in regard to improvement in vital sign abnormalities or symptoms present at enrollment, on Day 11.
6. To compare groups receiving azithromycin versus placebo in regard to new symptoms on Day 11, or deterioration in symptoms relative to the enrollment visit on Day 11.

3.2. Endpoints

3.2.1. Primary Endpoints

The primary endpoint is the efficacy of azithromycin versus placebo on Day 5 will be based on clinical improvement.

3.2.2. Secondary Outcome Measures

1. All antibiotic use from Day 1 through Day 11 and from Day 1 through Day 28 in each treatment group.
2. The proportion of subjects with one or more unplanned return visits to a physician's office or urgent care for persistent or worsening LRTI from Day 1 through Day 11 and from Day 1 through Day 28 in each treatment group.
3. The proportion of subjects with one or more emergency department visits for persistent or worsening from Day 1 through Day 11 and from Day 1 through Day 28 in each treatment group.
4. The proportion of subjects with one or more hospitalizations for persistent or worsening LRTI (if not hospitalized at the enrollment visit) from Day 1 through Day 11 and from Day 1 through Day 28 in each treatment group.
5. The proportion of subjects exhibiting improvement in at least one presenting symptom at Day 11 and at Day 28 in each treatment group.
6. The efficacy of azithromycin versus placebo on Day 11 will be based on clinical improvement.
7. The efficacy of azithromycin versus placebo on Day 28 will be based on clinical improvement.
8. Outcome assessed employing a superiority analysis using the RADAR approach.
 - The endpoint/outcome measure is the composite overall DOOR at Outcome Assessment on Day 5.
9. Proportion of subjects reporting solicited adverse events from Day 1 to Day 5 in each treatment group.
10. Proportion of subjects reporting one or more hospitalization or visits to an ED, outpatient clinic, or urgent care center (after randomization) for worsening or persistent LRTI from Day 1 through Day 5 in each treatment group.
11. The proportion of subjects exhibiting improvement in at least two presenting signs or symptoms at Day 5 in each treatment group.

12. The proportion of subjects exhibiting worsening or deterioration in at least one or more symptoms at Day 5 in each treatment group. The proportion of subjects with a new occurrence of a vital sign abnormality at Day 5 in each treatment group.

3.2.3. Exploratory Outcome Measures

1. Mean change in PCT levels from Day 1 and Day 5 among subjects in the placebo and azithromycin groups and among subjects with clinical improvement and clinical failures in each treatment group.
2. RADAR analysis at Day 11 (as described for Day 5 in Section 3.2.2 except temperature will be the only vital sign assessed at Day 11).
3. Proportion of subjects reporting solicited adverse events from Day 1 to Day 11 in each treatment group.
4. Proportion of subjects reporting one or more hospitalization or visits to an ED, outpatient clinic, or urgent care center for worsening or persistent LRTI from Day 1 through Day 11 in each treatment group.
5. The proportion of subjects exhibiting improvement in at least two presenting signs or symptoms at Day 11 in each treatment group.
6. The proportion of subjects exhibiting at least one new symptom on Day 11 in each treatment group. The proportion of subjects with a deterioration of one or more symptom relative to enrollment at Day 11 in each treatment group.

3.3. Study Definitions and Derived Variables

3.3.1. Timepoints

Day 5 Visit (D5V) represents Visit 3 which can occur any time from Day 5 to Day 8.

Day 11 Visit (D11V) represents Visit 4 which can occur any time from Day 11 to Day 14.

Day 28 Visit (D28V) represents Visit 5 which can occur any time from Day 26 to Day 30.

Day 1 is defined as the date of dose 1 for subjects treated with study product. For subjects not treated with study product, Day 1 will use their randomization date. The enrollment date will be used to define Day 1 for non-randomized subjects with PCT > 0.25 ng/mL. There is no Day 0 for this study, and the day preceding Day 1 will be reported as Day -1.

Study Day is defined relative to Day 1. If a visit did not occur, then study day will be imputed as its planned study day. Moreover, if a visit occurs out of the protocol defined window, then that visit will be treated as missing and its study day imputed as the planned study day in the Intention-to-Treat (ITT) analysis. Note that planned study day is 5 for D5V, 11 for D11V, and 28 for D28V.

3.3.2. Clinical Improvement at D5V

Clinical improvement at D5V is defined as fulfillment of **all** the following criteria.

1. Improvement in at least two symptoms present at enrollment (i.e., cough, sputum production, chest pain, or difficulty breathing) *or* one symptom and at least one vital sign abnormality present at enrollment. For symptoms, at least a one-step improvement (e.g., improvement from moderate to mild cough) will be considered a clinical improvement (Table 1). For vital sign abnormalities,

normalization of the presenting abnormal vital sign will be considered a clinical improvement. Qualifying vital signs and their normal values will include the following:

- temperature (<37.8°C or 100.0°F),
 - pulse (<90 bpm),
 - respiratory rate (≤20 breaths per minute),
2. Absence of deterioration in any qualifying symptom (i.e., cough, sputum production, chest pain, or difficulty breathing); or new vital sign abnormality not present at enrollment. For symptoms, at least a one-step deterioration (e.g. worsening from mild to moderate cough) will be considered clinical deterioration.
 3. Absence of fever in the day preceding or at the D5V (fever is defined as ≥37.8 °C or 100.0 °F, measured anywhere on the body).
 4. No medically attended visit to an ambulatory medical facility (e.g., ED, outpatient clinic, urgent care center) or hospitalization for persistent or worsening LRTI at any time after randomization (persistent or worsening LRTI is defined as receipt of a non-study antibiotic [parenteral or oral] treatment for LRTI or its complication). **Note:** receipt of a non-study antibiotic after study day 5 will not be regarded as satisfying this definition if it is related to a new non-respiratory process that is unrelated to the prior diagnosis of LRTI

Table 1: LRTI-Related Symptoms to Define Clinical Improvement Endpoint

	Mild	Moderate	Severe
Cough*	Occasional coughing (less than hourly)	Frequent coughing (1 or more times an hour and interferes with activity or sleep)	Almost constant coughing (never free of cough or need to cough, makes activity or sleep nearly impossible)
Sputum production*	Noticeable as a problem but does not interfere with activity	Causes a great deal of inconvenience	An almost constant problem
Chest pain	Noticeable only when coughing	Noticeable during deep breaths and when coughing	Almost constant, present even when resting, without cough
Difficulty breathing*	Noticeable during strenuous activity, such as going up a flight of stairs or walking more than a block on level ground	Noticeable during light activity, or when washing or dressing	Almost constant, present even when resting

*Modified from Breathlessness, Cough, and Sputum Scale (BCSS) [Christ-Crain, Stolz D et.al]

3.3.3. Clinical Improvement at D11V

Clinical improvement at D11V is defined as fulfillment of **all** the following criteria:

- For subjects who qualified based on the presence of at least two symptoms, then improvement must be observed in at least two symptoms present at enrollment (i.e., cough, sputum production, chest pain, difficulty breathing, or fever). For subjects who qualified based on the presence of one symptom and at least one vital sign abnormality, improvement must be observed in the one symptom present at enrollment. For symptoms other than fever, at least a one-step improvement (e.g., improvement from moderate to mild cough) will be considered a clinical improvement.
- **Note:** fever will be objectively (≥37.8 °C or 100.0 °F, measured anywhere on the body) or subjectively reported by the subject for the day preceding or on the D11V. For Day 11, fever will be

used similar to what has been done for Day 5 outcome measure definition i.e. clinical improvement requires absence of fever in the day preceding or at the D11V.

- **Note:** vital signs were not recorded at Days 11 and 28. Therefore, the subcomponents of clinical improvement at D11V and D28V are different from the subcomponents of clinical improvement used for the primary outcome measure at D5V (i.e., subcomponents at D11V and D28V do not include any reference to vital signs measures).
- Absence of deterioration in any qualifying symptom (i.e., cough, sputum production, chest pain, difficulty breathing, or fever). For symptoms other than fever, at least a one-step deterioration (e.g. worsening from mild to moderate cough) will be considered clinical deterioration.
- No medically attended visit to an ambulatory medical facility (e.g., ED, outpatient clinic, urgent care center) or hospitalization for persistent or worsening LRTI at any time after randomization (persistent or worsening LRTI is defined as receipt of a non-study antibiotic [parenteral or oral] treatment for LRTI or its complication). **Note:** receipt of a non-study antibiotic after study day 11 will not be regarded as satisfying this definition if it is related to a new non-respiratory process that is unrelated to the prior diagnosis of LRTI.

3.3.4. Clinical Improvement at D28V

Clinical improvement at D28V is defined as fulfillment of **all** the following criteria:

- Improvement in at least two symptoms present at enrollment (i.e., cough, sputum production, chest pain, difficulty breathing, or fever). For symptoms other than fever, at least a one-step improvement (e.g., improvement from moderate to mild cough) will be considered a clinical improvement.
- **Note:** fever will be objectively (≥ 37.8 °C or 100.0 °F, measured anywhere on the body) or subjectively reported by the subject for the day preceding or on the D28V.
- **Note:** vital signs were not recorded at Days 11 and 28. Therefore, the subcomponents of clinical improvement at D11V and D28V are different from the subcomponents of clinical improvement used for the primary outcome measure at D5V (i.e., subcomponents at D11V and D28V do not include any reference to vital signs measures).
- Absence of deterioration in any qualifying symptom (i.e., cough, sputum production, chest pain, difficulty breathing, or fever). For symptoms other than fever, at least a one-step deterioration (e.g. worsening from mild to moderate cough) will be considered clinical deterioration.
- No medically attended visit to an ambulatory medical facility (e.g., ED, outpatient clinic, urgent care center) or hospitalization for persistent or worsening LRTI at any time after randomization (persistent or worsening LRTI is defined as receipt of a non-study antibiotic [parenteral or oral] treatment for LRTI or its complication).

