  - Absence of deterioration in any qualifying symptom (i.e., cough, sputum production, chest pain, difficulty breathing, or fever). For symptoms other than fever, at least a one-step deterioration (e.g. worsening from mild to moderate cough) will be considered clinical deterioration (Table 1).
  - No medically attended visit to an ambulatory medical facility (e.g., ED, outpatient clinic, urgent care center) or hospitalization for persistent or worsening LRTI at any time after randomization (persistent or worsening LRTI is defined as receipt of a non-study antibiotic [parenteral or oral] treatment for LRTI or its complication). **Note:** receipt of a non-study antibiotic after study Day 11 will not be regarded as satisfying this definition if

it is related to a new non-respiratory process that is unrelated to the prior diagnosis of LRTI.

7. The efficacy of azithromycin versus placebo on Day 28 will be based on clinical improvement. Clinical improvement will be defined as fulfillment of **all** the following criteria:

- Improvement in at least two symptoms present at enrollment (i.e., cough, sputum production, chest pain, difficulty breathing, or fever). For symptoms other than fever, at least a one-step improvement (e.g., improvement from moderate to mild cough) will be considered a clinical improvement (Table 1).
- **Note:** fever will be objectively ( $\geq 37.8$  °C or 100.0 °F, measured anywhere on the body) or subjectively reported by the subject for the day preceding or on the Day 28 visit.
- **Note:** vital signs were not recorded at Days 11 and 28. Therefore, the subcomponents of clinical improvement at Day 11 and 28 are different from the subcomponents of clinical improvement used for the primary outcome measure at Day 5 (i.e., subcomponents at Day 11 and 28 do not include any reference to vital signs measures).
- Absence of deterioration in any qualifying symptom (i.e., cough, sputum production, chest pain, difficulty breathing, or fever). For symptoms other than fever, at least a one-step deterioration (e.g. worsening from mild to moderate cough) will be considered clinical deterioration (Table 1).
- No medically attended visit to an ambulatory medical facility (e.g., ED, outpatient clinic, urgent care center) or hospitalization for persistent or worsening LRTI at any time after randomization (persistent or worsening LRTI is defined as receipt of a non-study antibiotic [parenteral or oral] treatment for LRTI or its complication).

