### 5.1 Subject Inclusion Criteria

Subjects must meet all of the inclusion criteria to be enrolled in this study.

1. Clinician suspected LRTI based on the presence of at least two qualifying symptoms OR one qualifying symptom and at least one qualifying vital sign.

 LRTI will include acute bronchitis, tracheitis, tracheobronchitis, asthma exacerbation, and acute exacerbation of COPD but does not include known pneumonia.

 New cough, worsening of chronic cough, new sputum production, increased volume or purulence of chronic sputum production, chest pain, and difficulty breathing

 Fever (Provider or patient-measured temperature  $\geq 37.8^{\circ}\text{C}$  ( $100.0^{\circ}\text{F}$ ) or patient-reported feverishness), tachycardia of  $\geq 90$  beats/minute, tachypnea of  $>20$  breaths/minute

2. Males and females age  $\geq 18$  years old.
3. Presentation  $\geq 24$  hours and  $\leq 28$  days after the onset of at least one qualifying symptom related to the acute episode of illness.
4. Ability to understand study procedures and willing and able to comply with all required procedures and visits for the entire length of study.
5. Provide written informed consent before initiation of any study procedures.

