For subjects who qualified based on two symptoms, improvement in symptoms at D11V or D28V will be defined as presence of at least one-step improvement in two qualifying symptoms present at enrollment. For subjects who qualified based on one symptom and one vital sign abnormality, clinical improvement at D11V or D28V will be defined as the presence of at least one-step improvement in the one symptom present at baseline. If the one qualifying symptom at baseline has a missing value at D11V or D28V, then improvement in symptoms at D11V or D28V is missing, respectively.

Improvement in fever at D11V or D28V is defined as changing from presence of fever at baseline to absence of fever on D11V or D28V, respectively. Fever will be present at D11V if temperature reported on the LRS form for study day 11 is $\geq 100.0^{\circ}\text{F}$ or if subjective fever is recorded on the LRS form on study day 11. A subject has fever at baseline or at D28V if the subject had subjective fever or a temperature of $\geq 100.0^{\circ}\text{F}$ reported on the LRT form (i.e. LRTTMPF ≥ 100 or LRTFEVYN = Yes) for Visit 1 or Visit 5, respectively. If

at least some of the temperature information is available at D11V or D28V, but none of it indicates objective or subjective fever, then fever is absent at D11V or D28V respectively. If none of the temperature or fever information is available at D11V or D28V, then fever is missing at D11V or D28V, respectively.

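### The plan contains two incompatible definitions of Day 28 clinical improvement: SAP 3.3.4 and protocol 3.2.2(7) require two improved symptoms from everyone, while SAP 6.5.2.1 accepts one from one-symptom entrants

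*SAP*

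**What the plan says.** Entry: inclusion criterion 1 (protocol 5.1) admits subjects with two qualifying symptoms "OR one qualifying symptom and at least one qualifying vital sign". The qualifying signs are fever (measured or patient-reported), tachycardia and tachypnea.

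Day 28 definition: protocol 3.2.2(7) asks for "Improvement in at least two symptoms present at enrollment", and SAP 3.3.4 repeats it: "Improvement in at least two symptoms present at enrollment (i.e., cough, sputum production, chest pain, difficulty breathing, or fever". Neither makes an exception for one-symptom entrants. The list of countable items is the four respiratory symptoms plus fever. Pulse and respiratory rate cannot count, because "vital signs were not recorded at Days 11 and 28".

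Day 11 definition: protocol 3.2.2(6) and SAP 3.3.3 have two branches. Two-symptom entrants need two improvements. The other branch reads "For subjects who qualified based on the presence of one symptom and at least one vital sign abnormality, improvement must be observed in the" single symptom they had at enrollment.

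Derivation: SAP 6.5.2.1 covers both visits together and carries the second branch to Day 28. For subjects who qualified on one symptom and one vital sign, "clinical improvement at D11V or D28V will be defined as the presence of at least one-step improvement in the one symptom present at baseline".

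Use: Day 28 improvement is tested for non-inferiority in ITT and ATP-28 (protocol 11.4.2 item 3; SAP 8.2.2 and 8.2.3), with the 12.5-point margin that SAP 8.1.1 applies to all secondary non-inferiority analyses. The Table 25 shell prints a Yes/No conclusion. The variable also enters the exploratory longitudinal analyses that use Day 28 (SAP 8.3.10).

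**The concern.** A subject who enters with cough and tachycardia, has no fever, and is entirely well at Day 28 fails under SAP 3.3.4 and meets the symptom criterion under SAP 6.5.2.1. The same data give different endpoint values depending on which section the programmer follows.

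Two things are at stake. First, if the choice is still open when treatment codes are known, it becomes a post hoc choice of endpoint. Second, if 3.3.4 is followed, part of each arm cannot succeed whatever the treatment does. That distorts the Day 28 difference and makes Day 28 rates not comparable with Day 11 rates, where the one-symptom branch exists.

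**Working it through.** The documents state no figure for this point, so there is nothing to reproduce. The check has two parts: logic, then size.

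**1. Who is blocked under each rule**

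Inputs: four symptoms (cough, sputum production, chest pain, difficulty breathing) and three signs (fever, tachycardia, tachypnea), each present or absent at baseline.

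- Eligible on two or more symptoms: (6 + 4 + 1) symptom patterns × 8 sign patterns = 88.
- Eligible on exactly one symptom and at least one sign: 4 × 7 = 28.
- Total eligible patterns: 88 + 28 = 116.

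Under SAP 3.3.4 a subject can succeed only if symptoms plus fever number at least two. This fails for one symptom, no fever, and tachycardia only, tachypnea only, or both: 4 × 3 = 12 of 116. Under SAP 6.5.2.1 it fails for 0 of 116. These are counts of patterns, not shares of subjects.

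**2. Size if SAP 3.3.4 is programmed**

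Let s be the share of blocked subjects in each arm. The documents do not give s; 5%, 10% and 15% are illustrative. If the treatment effect is the same in the blocked group as elsewhere, a true difference d is observed as d × (1 − s):

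- s = 5%: 12.5 × 0.95 = 11.9 points
- s = 10%: 12.5 × 0.90 = 11.25 points
- s = 15%: 12.5 × 0.85 = 10.6 points

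The probability of concluding non-inferiority, by the unpooled normal approximation, is Φ[(0.125 − difference)/SE − 1.96], where SE = √[(pA(1 − pA) + pP(1 − pP))/337]. The 337 per arm is the planned randomized number (protocol section 5). The Day 28 rates are assumptions.

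*Placebo truly worse by the margin* (80% vs 67.5% among those able to succeed):

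| s | Rates | Difference | SE | P(conclude NI) |
|---|---|---|---|---|
| 0 | 80.0 / 67.5 | 12.5 | 0.0335 | 2.5% |
| 5% | 76.0 / 64.1 | 11.9 | 0.0350 | 3.7% |
| 10% | 72.0 / 60.75 | 11.25 | 0.0361 | 5.3% |
| 15% | 68.0 / 57.4 | 10.6 | 0.0370 | 7.3% |

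*Arms truly equal* (80% in both among those able to succeed):

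- s = 0: half-width of the interval 1.96 × √(2 × 0.80 × 0.20/337) = 6.0 points; P(conclude NI) = 98.2%.
- s = 10%: both rates are 72%; half-width 1.96 × √(2 × 0.72 × 0.28/337) = 6.8 points; P(conclude NI) = 95.1%.

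So the effect runs in opposite directions in the two settings.

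**The case against.** The strongest reply is that SAP 6.5.2.1 is the operational text: it names the forms and handles missing values, so it is the part most likely to be programmed. If it is, nobody is blocked and nothing is attenuated. That stands, and it makes the harm conditional. It does not remove the contradiction, because the analysis would then depart from the protocol's Day 28 definition and from the SAP's own definitions section. SAP section 13 lists only added exploratory and bivariate analyses, not this change.

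Three stronger readings are tempting, and the documents do not support them.

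- A reader might infer that anyone enrolled on one symptom plus tachycardia or tachypnea can never succeed at Day 28. That is so only under 3.3.4, and only without fever. Subjective fever counts as baseline fever in 6.5.2.1, so a subject who also felt feverish has two countable items.
- A reader might infer that guaranteed failures always favour non-inferiority. They do near the margin. With equal arms and a high success rate they widen the interval and reduce power.
- A reader might infer that the trial's conclusion is exposed. SAP 8.1.1 reserves the non-inferiority conclusion for the Day 5 primary analysis and calls the others supportive.

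It is also fair to say that nothing in the documents informs the 5 to 15% range.

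**Conclusion.** The inconsistency is certain: protocol 3.2.2(7) and SAP 3.3.4 on one side and SAP 6.5.2.1 on the other cannot both define Day 28 improvement. The consequence is conditional on 3.3.4 being programmed. Its size rests on an unknown share of affected subjects, an equal treatment effect in that group and, for the probabilities, assumed Day 28 rates of 80% and 67.5%. On those terms the chance of a false non-inferiority finding at the margin rises from 2.5% to between 3.7% and 7.3%; with equal arms at 80%, power falls from 98.2% to 95.1% at a 10% share. The reach is the Day 28 non-inferiority analyses in ITT and ATP-28 and the exploratory longitudinal analyses that use Day 28. It should be corrected, but it does not bear on the primary result.

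**What to change.** Before unblinding, replace the single symptom criterion in protocol 3.2.2(7) and SAP 3.3.4 with the two-branch criterion already used for Day 11, so that both match SAP 6.5.2.1. Record the change, dated and made blind to treatment, in SAP section 13. The number of subjects affected can be counted from blinded baseline data, since SAP 6.5.2 already classifies each subject's route of entry and takes baseline severity from the Visit 1 form.

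No new data are needed, but this is more than an editorial change: it alters a secondary endpoint definition in the protocol, and protocol 14.2 requires amendments to go to the IRB before implementation. It also loosens the rule for one group. Subjects enrolled on one symptom plus fever must improve in both under 3.3.4, but only in the symptom under the Day 11 branch. Fever still counts in the Day 28 deterioration criterion. The Day 11 text also has a note requiring absence of fever that the Day 28 text lacks; the amendment should say whether that note is meant to apply at Day 28.
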